8.2. Detailed Analysis Plan

The Novoglan-01 clinical trial involves the following measurement variables, which will be measured pre- and post-treatment:

Primary outcome variable (ordinal, scalar): Kikiros-inspired phimosis assessment scale (Kikiros, Beasley & Woodward 1993)

Secondary outcome variable (ordinal, scalar): A standardized treatment tolerability questionnaire

Secondary outcome variable (ordinal, scalar): A QoL scale questionnaire

The trial will also involve descriptive variables collected for each patient:

Physical parameters (e.g. age, weight, height – numerical variables)

Medical history (categorical, binary)

Record of Adverse Events (categorical, binary)

Evaluating Patient Descriptive Variables

The recommended analysis plan for the descriptive variables is to use a univariate analysis to contribute to the descriptive statistics of N. From there, tables showing frequency with medians, range, and standard deviations can be generated to describe the population.

Evaluating the Primary and Secondary Outcome Variables

An initial validation of each primary and secondary outcome variable will be applied using the Principal Component Analysis. If this analysis is successful, then each variable will be evaluated in an ordinal regression model (De Leeuw, Mair & Groenen 2017). If the outcome variables are to be evaluated at the same time, then a Multivariate Multinomial Logit Model will be applied (Bel & Paap 2014).

Further tests may be applied to evaluate any distributions and homogeneity within and between descriptive and outcome variables such as a Chi-Squared Test, Linear-by-linear Association Test, or Mann-Whitney U Test.

REFERENCES

- Bel, K. & Paap, R. 2014, A Multivariate Model for Multinomial Choices.
- R Development Core Team 2017, *R: A Language and Environment for Statistical Computing*, Vienna, Austria., R. Found. Stat. Comput., vol. 1.

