3.2. Secondary Objectives

The first of secondary objectives is to assess the safety of the Novoglan treatment by observing and reporting any treatment discomfort or adverse event mentioned by the participants during the treatment.

The second of secondary objectives is to confirm the participant satisfaction with the Novoglan treatment by assessing the improvement of quality of life reported by the participant and the treatment tolerability as reported by the participant at the end of the trial.

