NOTE: During the phoned Study Visit 3 the participant will be offered the option to schedule a face-to-face follow-up training with the Clinical Trial Nurse at Macquarie University Hospital. If carried out, the outcome of such a follow-up training will be recorded in the Study Visit 3 Case Report Form.

Final Study Visit

At the Final Study Visit, the participant will initially meet with the Clinical Trial Nurse and subsequently with the Principal Investigator, [name].

The Clinical Trial Nurse will investigate and record in the participant Case Report Form the following information:

- Measurement of the participant phimosis at study end using the Novoglan-01 Study Phimosis Measurement Form (see details further in Section 9)
- Evaluation of the participant quality of life at the end of treatment and using the Novoglan-01 Quality of Life Questionnaire (see details further in Section 9)
- Evaluation of the participant perceived tolerability of the Novoglan product during the treatment and using the Novoglan-01 Novoglan Treatment Tolerability Questionnaire (see details further in Section 9)

After meeting with the Clinical Trial Nurse, the participant will meet with the Principal Investigator, [name], to review the outcomes of his Novoglan treatment and sign the Novoglan-01 Participant Completion section on the Final Study Visit case report form (see details in Section 9).

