6.9. Participant Withdrawal

The voluntary participant withdrawal during the Novoglan-01 Study Protocol follows the guidelines from the ***National Statement on Ethical Conduct in Human Research*** (2007, updated 2018).

Voluntary withdrawal

Participants enrolled in the Novoglan-01 clinical trial are entitled to withdraw at any stage. Before consenting to be involved in the Novoglan-01 study, participants will be informed about any consequence of such withdrawal. The withdrawal of any participant will be registered by the signature by both the Principal Investigator and the withdrawing Participant of the ***Novoglan-01 – Form for Withdrawal of Participation*** attached to this study protocol. Participants withdrawing prior to visit 1 where investigative product and training is provided will be replaced.

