7. OUTCOMES

7.1. Definition of Outcomes

The expected outcomes from the Novoglan-01 study are as follows.

- Confirmation of the ability of the Novoglan product to effectively relieve phimosis as measured by foreskin retraction before and after treatment against the Phimosis Measurement Scale used at Study Visit 1 and Final Study Visit.
- Confirmation of the safety of the Novoglan treatment as evidenced by the lack of any severe adverse effect or any complication during treatment.
- Confirmation of the satisfaction of participants with the Novoglan treatment as measured by improved quality of life measured by questionnaire filled in by the participants before and after treatment.
- Confirmation of the tolerability of the Novoglan treatment as measured by the treatment tolerability questionnaire filled in by the participants during the Final Study Visit.
- Confirmation of the Novoglan treatment as a valid conservative first line treatment alternative to steroid creams in adult males presenting with phimosis.

Additionally, the publication of the Novoglan-01 study results at urology conferences and in a peer review journal is likely to encourage a review of clinical recommendations in the treatment of adult phimosis. Phimosis treatment guidelines published by the British Association of Urological Surgeons (BAUS) discourage the manual stretching of the foreskin and recommend the use of steroid creams or circumcision. The professional guidelines from the BAUS also refer physicians to the guidelines published by the European Association of Urology (EAU) which address phimosis in the section dedicated to paediatric urology.

Assuming a positive outcome from the Novoglan-01 study that demonstrates the safety, efficacy and tolerability of the Novoglan product in adult phimosis, the aim would be to:

- Convince the phimosis treatment guidelines published by the Urology Society of Australian and New Zealand (USANZ), EAU or BAUS to include a section dedicated to the treatment of adult phimosis.
- Convince the phimosis treatment guidelines published by the USANZ, EAU or BAUS to list the Novoglan product as a recommended conservative treatment for adult phimosis

Finally, the publication of the Novoglan-01 study results is likely to position MQ Health as the centre of reference for adult phimosis treatment in Australia. It is also likely to stimulate similar studies in Australia and overseas.

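### Section 8.2 lists tolerability as measured before and after treatment, but it is collected once, at the Final Study Visit, and is not scheduled for men who withdraw after receiving the device

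*Protocol*

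**What the plan says.** Section 8.2 opens with a list of "the following measurement variables, which will be measured pre- and post-treatment". The list has three entries: the phimosis scale, "A standardized treatment tolerability questionnaire", and a quality-of-life questionnaire. All three then go through the same steps, a principal component analysis followed by ordinal regression. Tolerability has no separate treatment as a single-time-point outcome.

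The rest of the protocol gives tolerability one time point:

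- Section 3.2 speaks of "treatment tolerability as reported by the participant at the end of the trial".
- The schedule table in section 6.2 ticks the questionnaire only under the Final Study Visit (Week 7 to 9). The visit description there calls it "Evaluation of the participant perceived tolerability of the Novoglan product during the treatment".
- Section 6.8 lists it among the end-of-treatment surveys. It refers back to Visit 1 for phimosis and quality of life, but not for tolerability.
- Section 7.1 names the "treatment tolerability questionnaire filled in by the participants during the Final Study Visit".

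On men who leave, section 6.9 says "Participants enrolled in the Novoglan-01 clinical trial are entitled to withdraw at any stage". It records withdrawal by a form signed by the participant and the Principal Investigator, and it replaces only those who leave before Visit 1. Section 8.1 plans for 20% drop-out.

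**The concern.** There are two linked problems. First, section 8.2 states a measurement that cannot be made, because before Visit 1 there is no treatment to rate. Anyone building the data set or the model from 8.2 would expect a baseline tolerability value and find none.

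Second, a questionnaire given only at the Final Study Visit is answered only by men who attend it. Men who withdraw after receiving the device have no scheduled score, and poor tolerability is an obvious possible reason for leaving. An analysis plan can choose how to treat missing scores, but it cannot supply scores that were never collected.

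Tolerability matters to the trial's claim. It is part of the section 2 hypothesis and of the second secondary endpoint in section 4.4, and section 7.1 expects the trial to confirm it as part of a case for changing treatment guidelines.

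**Working it through.** **Step 1. Timing of each instrument, section by section.**

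| Instrument | Timing in 8.2 | Timing in 6.2 and 6.8 |
|---|---|---|
| Phimosis scale | before and after | Visit 1 and Final Study Visit |
| Quality of life | before and after | Visit 1 and Final Study Visit |
| Tolerability | before and after | Final Study Visit only |

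Section 8.2 implies two tolerability measurements per man, and the schedule gives one. Section 4.4 agrees with the schedule: it attaches before-and-after measurement to quality of life only. Section 6.2 has the device first supplied at Visit 1, which rules out an earlier tolerability score.

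**Step 2. The protocol's drop-out figure.** Inputs from section 8.1: N = 24, drop-out 20%, 29 to be recruited.

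- 24 × 1.20 = 28.8, rounded up to 29, which reproduces the stated figure.
- Dividing instead gives 24 / 0.80 = 30. The one-man difference does not affect this point.

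**Step 3. Men without a score.**

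- With 29 recruited: 29 × 0.20 = 5.8 without a score and 29 × 0.80 = 23.2 with one. The planned margin itself is 29 - 24 = 5.
- With 24 enrolled, the number given in section 4.2: 24 × 0.20 = 4.8 without a score.

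So about five or six men would have no score if the drop-out falls after Visit 1. The protocol does not split the 20% by timing.

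**Step 4. Effect on the result (illustration).** Assumptions not in the protocol: 29 men supplied, 5 leave after supply, the ordinal questionnaire is reduced to good or not good, and 22 of 24 attendees report good tolerability.

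- Attendees: 22/24 = 91.7%.
- All supplied, if none of the 5 tolerated the device: 22/29 = 75.9%. Difference 91.7 - 75.9 = +15.8 points.
- All supplied, if all 5 tolerated it: (22 + 5)/29 = 27/29 = 93.1%. Difference 91.7 - 93.1 = -1.4 points.

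The attendee figure can therefore differ from the all-supplied figure by about -1 to +16 points.

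**Step 5. Sensitivity to the drop-out rate.** Let p be the proportion with good tolerability among attendees and d the drop-out after supply. The all-supplied proportion lies between p(1 - d) and p(1 - d) + d. With p = 0.90 (assumed):

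| d | Lowest | Highest |
|---|---|---|
| 10% | 81% | 91% |
| 20% | 72% | 92% |
| 30% | 63% | 93% |

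The possible overstatement grows with drop-out, while the possible understatement stays small.

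**The case against.** The strongest reply is that only the lead-in sentence of 8.2 is wrong. The other sections that give a timing agree with each other, and staff who follow the schedule will collect the questionnaire at the right visit. A reader might infer that 8.2 prescribes a before-after test of tolerability that cannot be run. The text does not go that far: it names no change score or paired test, only principal component analysis and ordinal regression. What cannot exist is the pre-treatment measurement.

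A reader might also infer that men who stop using the device never answer. Section 6.9 concerns withdrawal from the study, and nothing makes attendance at the Final Study Visit depend on continued use. A man who stops but stays enrolled can attend and answer.

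Discomfort is not ignored either. Section 3.2 makes it part of the safety objective, and the two phone visits ask about progress, problems and adverse effects. Early intolerance may therefore appear in the safety data. It does not enter the tolerability outcome, which is the questionnaire.

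The withdrawal form and the Statistical Plan are attachments that are not shown. The form may ask for a reason, and the plan may settle the denominator and the intervals. This limits how much can be said about analysis. It does not remove the gap, because the schedule and section 6.9 place no tolerability assessment at withdrawal.

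Finally, it is tempting to say that the result is biased in favour of the device. The direction is not certain. Section 1 reports apparent relief in 3 to 4 weeks, so some satisfied men might also fail to return for a visit at Week 7 to 9.

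**Conclusion.** The contradiction in timing is certain: section 8.2 conflicts with sections 3.2, 6.2, 6.8 and 7.1, and a pre-treatment tolerability score is impossible. The collection gap also stands. As written, the protocol yields a tolerability result for Final Study Visit attendees, with no scheduled score from men who withdraw after receiving the device, about five or six at the planned drop-out rate.

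That result may be biased, probably in favour of the device because poor tolerability is a natural reason to leave, but the documents do not establish the direction. The range of -1 to +16 points rests on the assumed 22 of 24, on a good/not-good cut that the protocol does not define, and on all five losses falling after supply. Men who leave before Visit 1 are replaced and do not contribute. The point concerns a secondary outcome. It should be corrected, and it does not affect the primary endpoint.

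**What to change.** 1. In 8.2, limit the before-and-after statement to the phimosis scale and quality of life, and describe and analyse tolerability as a single post-treatment outcome.
2. In the 6.2 table and in 6.9, offer the existing tolerability questionnaire, together with a question on the reason for leaving, to men who withdraw after Visit 1, by phone if needed. If the withdrawal form already asks for the reason, say so in 6.9.
3. Report tolerability for all men supplied with the device and state how many scores are missing. Add a sensitivity analysis that counts men who left because of discomfort as not tolerating the device. This is one reasonable choice among several, and it should be fixed before the data are seen.

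The cost is some protocol wording and one short existing form for about five or six men. Withdrawing men remain free to decline it, so some scores may still be missing. The reported figure may be less favourable than one based on attendees alone.

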4.2. Expected Participant Numbers

The Novoglan-01 study is expected to enroll 24 participants.

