4.4. Endpoints

Primary Endpoints

Primary endpoint – Efficacy of the device demonstrated by the improvement in foreskin retraction as measured using the Kikiros-inspired phimosis assessment scale.

Secondary Endpoints

First secondary endpoint – Safety of the device as evidenced by the reporting of any adverse effect or complication as observed and noted by the clinical trial team during the participant's treatment.

Second secondary endpoint – Participant satisfaction with the treatment as confirmed by treatment tolerability reported by the participant with a standardised treatment tolerability questionnaire and improvement in quality of life post-treatment as assessed by a standardised quality of life questionnaire before and after treatment.

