8.1. Sample Size or Power Calculation

A power calculation was performed to assess which sample size (N) was appropriate for the Novoglan-01 clinical trial. Calculations show that 29 participants must be recruited to reach N = 24, considering a potential drop-out rate of 20%.

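### Outcome modelling is made conditional on a successful principal component analysis, which cannot validate a single-grade primary outcome and should not gate any outcome

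*Protocol*

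**What the plan says.** Section 4.4 of the protocol defines the primary endpoint as "improvement in foreskin retraction as measured using the Kikiros-inspired phimosis assessment scale". Section 8.2 lists it as "Primary outcome variable (ordinal, scalar): Kikiros-inspired phimosis assessment scale", and Section 7.1 has it compared before and after treatment "against the Phimosis Measurement Scale used at Study Visit 1 and Final Study Visit". The secondary outcomes include a tolerability questionnaire and a quality of life questionnaire.

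For the analysis, Section 8.2 states: "An initial validation of each primary and secondary outcome variable will be applied using the Principal Component Analysis". The next sentence is the condition: "If this analysis is successful, then each variable will be evaluated in an ordinal regression model". A later paragraph allows further optional tests of distributions and homogeneity. These are not tied to the outcome of the PCA.

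On numbers, Section 4.2 says "The Novoglan-01 study is expected to enroll 24 participants". Section 8.1 says "Calculations show that 29 participants must be recruited to reach N = 24, considering a potential drop-out rate of 20" (per cent). Sections 6.7 and 13 describe the study as open label. Section 9.4 has the data collated and analysed once accrual is complete. Section 8 introduces its content as a summary of the main points of a separate Statistical Plan, which is not available here.

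**The concern.** A condition placed before the primary analysis should bear on whether that analysis is appropriate, and its result should not depend on who reads it. This one does neither. PCA describes how several measured variables vary together. It does not show that an instrument measures what it is meant to measure, and it carries no information on whether participants improved. The primary outcome is one grade per visit, so there is almost nothing for PCA to work on.

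What is at stake is control over which outcomes are modelled. The step is run on the full trial data, after collection, in a study where nobody is blinded. If an outcome can be kept or set aside at that point, the set of reported results depends in part on the data, and nothing in the protocol controls for that selection.

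**Working it through.** **Inputs.** N = 24 (Sections 4.2 and 8.1). The primary outcome is one scalar grade (8.2), measured twice (7.1). The questionnaire item counts, the component-retention rule, the pre-post correlation r and the proportion reaching the final grade are not in the protocol. They are assumptions below, shown over a range.

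**The plan's own figure.** The only computed figure in Section 8.1 is 29 recruits for N = 24. It reproduces as 24 × 1.2 = 28.8, rounded up to 29 (24/0.8 would give 30, and 29 × 0.8 = 23.2). N = 24 itself cannot be re-derived, because no alpha, power or effect size is stated. The point below does not depend on the 29.

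**Step 1: the grade as a single variable.** The correlation matrix is 1 × 1 with entry 1. Its one eigenvalue is 1, and the share explained is 1/1 = 100% whatever the data. The check cannot fail and tests nothing.

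**Step 2: pre and post grades as two columns.** The correlation matrix has eigenvalues 1 + r and 1 − r. The first-component share is therefore (1+|r|)/2, never below 50%. Simulated at n = 24 (normal data, 20,000 runs):

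| True r | (1+r)/2 | Central 95% range of observed share |
|---|---|---|
| 0 | 0.50 | 0.50–0.73 |
| 0.3 | 0.65 | 0.51–0.82 |
| 0.5 | 0.75 | 0.57–0.88 |
| 0.7 | 0.85 | 0.71–0.93 |

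This is the pre-post correlation on another scale. PCA centres each column, so moving every post-treatment grade by the same amount leaves r and both eigenvalues unchanged. That shift is what the primary endpoint measures.

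**Step 3: when everyone finishes at the same grade.** The post column then has zero variance, r is 0/0, and PCA on the correlation matrix is undefined. The background text before Section 1.2 reports a very high success rate and treatment continuing until full retraction, so this outcome is possible. If each participant independently reaches the same final grade with probability p, the chance that all 24 do is p^24:

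- p = 0.90: 0.90^24 = 8%
- p = 0.95: 0.95^24 = 29%
- p = 0.98: 0.98^24 = 62%

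**Step 4: questionnaires.** Simulation with 24 respondents and wholly unrelated items (normal data, 5,000 runs per item count):

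| Items (assumed) | Mean largest eigenvalue | Mean number of eigenvalues above 1 |
|---|---|---|
| 3 | 1.33 | 1.4 |
| 5 | 1.61 | 2.3 |
| 10 | 2.19 | 4.4 |
| 20 | 3.11 | 8.2 |

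With five-level items in place of normal data (2,000 runs), 5, 10 and 15 items give on average 2.3, 4.5 and 6.4 eigenvalues above 1. The first component takes 32%, 22% and 18% of the variance, against 20%, 10% and 6.7% expected. A rule that retains eigenvalues above 1 would find components in noise.

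A different rule behaves differently. If success meant one dominant component, then with 10 five-level items the central 95% range of the first-component share is 18–26% for unrelated items, 25–49% for inter-item correlation 0.3, and 37–65% for 0.5. The first and last ranges do not overlap. The answer therefore depends heavily on a rule that the protocol does not name.

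**The case against.** Several stronger readings are tempting, and the documents do not support them.

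- **The primary endpoint could go unanalysed.** On the single-grade reading the check is always passed, so it cannot block anything and is merely redundant. It can break down only on the two-column reading of Step 3. Even there, a fallback may be in the Statistical Plan, which Section 8 only summarises.
- **The missing success criterion is itself the fault.** A definition may also be in that plan, so its absence from the protocol is no finding. The stated condition is a different matter. It is presented as a main point of the plan, and no definition of success would make a PCA of one grade bear on efficacy.
- **The condition invalidates the stated error rate.** The protocol states none. Section 8.1 says only "A power calculation was performed to assess which sample size (N) was appropriate for the Novoglan-01 clinical trial". What can be said is that selection through this step is uncontrolled.
- **PCA with 24 respondents is uninformative, and noise always passes.** That follows only under the assumed eigenvalue rule and item counts. Under a dominant-component rule, strongly correlated items separate from noise (Step 4). Imprecise is the fair word.

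Two further points for the sponsor deserve weight. The phimosis measurement form is not shown, and if it held several items a PCA would not be strictly empty; Section 8.2, however, calls the outcome scalar. Section 11.1 also has staff sign a declaration committing them to unbiased analysis and publication, and Section 7.1 lists every outcome for confirmation. Both make deliberate dropping of an outcome less likely, but neither removes a rule that allows it.

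**Conclusion.** The condition in Section 8.2 is wrong as written. For the primary outcome it is either trivial (100% by construction) or a restatement of the pre-post correlation that is blind to improvement. In the second form it is undefined if all participants reach the same final grade, with probability 8% to 62% under assumed per-participant rates of 90% to 98%. For the questionnaires PCA has some content but is imprecise at about 24 respondents, and passing or failing depends on the rule chosen. Because it would be judged on complete open-label data, the step could decide which outcomes are modelled.

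This rests on the outcome being a single grade, as Section 8.2 describes it, and on assumed item counts, retention rules and success rates. The core of the point does not need the last three: an efficacy analysis should not hang on a step that says nothing about efficacy.

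**What to change.** Delete the PCA condition from Section 8.2 and from the Statistical Plan. In its place:

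- Name one paired ordinal analysis of the pre-post change in phimosis grade as the primary analysis.
- State that the primary endpoint and both questionnaire outcomes are analysed and reported for all participants with data, whatever any scale check shows.
- If a check on the questionnaires is wanted, report it descriptively (PCA, or Cronbach's alpha with its confidence interval, which will also be imprecise at this size) and state that it gates nothing.

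The cost is an amendment to the wording of the two documents, processed as Section 10.3 provides. Sample size, visits and data collection do not change.

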recommend the use of steroid creams or circumcision. The professional guidelines from the BAUS refer physicians to the guidelines published by the European Association of Urology (EAU) [EAU Guidelines, 2016] which address phimosis in the section dedicated to paediatric urology. The treatment recommendations include the use of steroid creams and if unsuccessful, the circumcision of the penis.

The main problem with using steroid creams to treat phimosis is the narrow range of stretching motion that will provide suitable stimulation for the foreskin to grow without exacerbating the inflammation or tearing of the foreskin. Recently, a new conservative treatment option, the Novoglan product, has shown promising results, with a very high success rate and satisfaction reported by users. The Novoglan product is designed to be used by participants 18 years and over. Its main component is a small balloon that can be inserted underneath the opening of the foreskin and progressively inflated while avoiding the complications frequently observed with the use of steroid creams. The Novoglan balloon is guided under the foreskin between the glans and the inner side of the foreskin (prepuce) using a purpose moulded rod. Once the balloon is in place the rod is removed and the stop cock and plunger is attached to the Novoglan device. The balloon is inflated by pressing the plunger. The procedure is painless and pressure is under the control of the user to ensure no discomfort. Foreskin cells are placed under tension and tight junctions are loosen under stretching leading to tissue adaptation and cell mitosis. This process increases the column of foreskin cells and increases the foreskin circumference. Treatment is continued for a period of 4 to 8 weeks until full normal retraction is achieved.

The Novoglan product is a medical device commercialised in Australia since 2006 and listed with the Australian Therapeutics Goods Administration (ARTG 168962). The Novoglan product has been used successfully in the Urology Clinic in the past year at Macquarie University Hospital but only with a few adult male participants. The observation of these few adult participant treatments indicated that the Novoglan product is simple and safe to use, effective at treating adult phimosis and comparatively inexpensive. It appears that the Novoglan product produces relief from the symptoms of phimosis in 3 to 4 weeks.

References, in order of citation, are as follows.

The prepuce.

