5. STUDY PARTICIPANTS

5.1. Inclusion Criteria

The Novoglan-01 study inclusion criteria are as follows.

1. Male 18 or older referred to the urology clinic
2. Symptoms of adult phimosis with inability to fully retract the foreskin
3. Reporting of pain or discomfort

4. Potential participant may have Balanitis Xerotica Obliterans or undergone prior frenuloplasty
5. Willingness to provide informed consent and willingness to participate and comply with the study requirements.

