8. STATISTICAL CONSIDERATIONS

[name] in a Note-To-File dated 15 September 2020 has decided to appoint [name] as biostatistician to the Novoglan-01 study. The credentials of [name] as a staff member of Macquarie University will better address the requirement for a highly professional and experienced biostatistical analysis of the Novoglan-01 study results than what [name] could provide.

In view of the cohort size of 24 participants and in view of the single arm, observational nature of the Novoglan-01 study, it is reasonable to consider the statistical analysis of the Novoglan-01 study as relatively simple. It has been documented by the study biostatistician in a controlled document stored in the Trial Master File and entitled “**Novoglan-01 clinical study – Statistical Plan**”. This document is attached to the Novoglan-01 Protocol. The main points of this document are summarised as follows.

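### If the three outcomes are analysed jointly, Section 8.2 prescribes a multinomial logit that 24 men cannot support unless every scale is collapsed to two or three levels

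*Protocol*

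**What the plan says.** Section 8.2 of the protocol lists phimosis grade, treatment tolerability and quality of life as ordinal outcomes. The entry for the first reads "Primary outcome variable (ordinal, scalar): Kikiros-inspired phimosis assessment scale". It introduces all three as measured both before and after treatment.

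The default analysis takes one outcome at a time, after a principal component step: "If this analysis is successful, then each variable will be evaluated in an ordinal regression model". For a joint evaluation one method is fixed: "If the outcome variables are to be evaluated at the same time, then a Multivariate Multinomial Logit Model will be applied".

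The rest of the setting comes from elsewhere in the protocol:

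- **Size.** Section 4.2: "The Novoglan-01 study is expected to enroll 24 participants". Section 8.1: "Calculations show that 29 participants must be recruited to reach N = 24, considering a potential drop-out rate of 20"%. Section 8 calls the analysis relatively simple, partly for this reason: "In view of the cohort size of 24 participants".
- **Eligibility.** Section 5.1, criterion 2: "Symptoms of adult phimosis with inability to fully retract the foreskin".
- **Treatment goal.** The background section says that treatment continues "until full normal retraction is achieved".
- **Timing of tolerability.** The visit table and the Final Study Visit text in Section 6.2, and Sections 6.8 and 7.1, place this questionnaire at the Final Study Visit only.

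The protocol does not give the number of levels of any scale, the covariates of the joint model, or the form of its association terms.

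**The concern.** A multinomial logit treats categories as unordered and spends a separate coefficient on each. Joining three such outcomes adds association terms that grow with the product of the level counts. In 24 men this leaves very little data per parameter, and some estimates may not exist.

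Two features of the protocol make this worse. Tolerability has no pre-treatment value, so the three outcomes are observed together only once per man. And eligibility leaves the fully retracting grade empty before treatment, although that grade is the stated goal of treatment.

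If the rule were followed, the software would report non-convergence, or large arbitrary coefficients with huge standard errors. A joint statement on efficacy, quality of life and tolerability drawn from that fit would be unsound, in a study that aims to influence treatment guidelines.

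**Working it through.** **1. Cohort size.** The recruitment figure in Section 8.1 reproduces as 24 × 1.20 = 28.8, rounded up to 29. (Dividing instead, 24 / 0.80 = 30.) The analysed number is taken as 24.

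**2. Parameters (K assumed, equal for the three outcomes).** The protocol does not write the model out, so the usual form with unrestricted pairwise associations is assumed.

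- Margins: 3(K−1). Associations: 3(K−1)².
- A pre/post term can apply only to phimosis and quality of life, which adds 2(K−1).

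| K | Margins + associations | With pre/post term |
|---|---|---|
| 3 | 6 + 12 = 18 | 18 + 4 = 22 |
| 4 | 9 + 27 = 36 | 36 + 6 = 42 |
| 5 | 12 + 48 = 60 | 60 + 8 = 68 |
| 6 | 15 + 75 = 90 | 90 + 10 = 100 |

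Unequal scales can need fewer. Levels of 4, 3 and 3 give margins 3 + 2 + 2 = 7 and associations 6 + 6 + 4 = 16, so 23 in all.

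**3. Records.** Phimosis and quality of life are each measured twice, which gives up to 48 man-visits. Tolerability is measured once. Complete three-outcome records therefore number at most 24, all post-treatment, and a three-outcome pre/post model cannot be formed.

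**4. Empty pairwise cells.** With unrestricted associations, an empty cell in a pairwise table means that its association estimate is not finite. Each table pairing tolerability with another outcome has c = K² cells and at most 24 men. If men spread evenly over the cells, the most favourable case,

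P(at least one empty cell) = 1 − Σⱼ (−1)ʲ C(c, j) (1 − j/c)²⁴.

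- K = 3, c = 9: 45% per table.
- K = 4, c = 16: 99.5%.
- K = 5, c = 25: certain, since 25 cells exceed 24 men.

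If all 29 recruits completed, the same formula with exponent 29 still gives 96% at K = 4.

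**5. The full-retraction grade.** Suppose visit is a covariate. For one outcome the pre/post coefficient of a grade against a reference grade is

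ln[(post count in grade / post count in reference) / (pre count in grade / pre count in reference)].

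Criterion 2 makes the pre-treatment count in full retraction zero. As soon as one man reaches that grade, the coefficient has no finite value. An illustrative table of 24 men with four grades, worst to full retraction, is 12, 8, 4, 0 before and 2, 4, 6, 12 after (counts assumed):

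- Second grade against worst: ln[(4/2)/(8/12)] = ln 3 = 1.1, finite.
- Third grade against worst: ln[(6/2)/(4/12)] = ln 9 = 2.2, finite.
- Full retraction against worst: ln[(12/2)/(0/12)], not finite.

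A numerical fit shows the same. At 5, 10 and 20 Newton steps the last coefficient is 7.8, 12.8 and 24.1, with standard errors of 5.9, 71 and 20,563. Its profile log-likelihood keeps rising (−54.05 at 4, −53.05 at 10, −53.046 at 20). The other two keep a standard error of 1.0.

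**6. Contrast with the ordinal model.** A proportional-odds fit to the same table converges, with log-odds 2.85 and standard error 0.66. It treats the 48 observations as independent, so it shows only that the estimate exists and is no model for the paired analysis.

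**The case against.** **The model is optional.** It applies only if the outcomes are evaluated together, and separate ordinal regression is already the default. This stands and lowers the severity. It does not remove the point, because the trigger is conditional but the method is not.

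**A reader might infer that the model can never be estimated because it has more parameters than men.** The protocol does not support that. It gives no level counts. Two or three levels per scale, or mixed lengths such as 4, 3 and 3, stay below 24 before any pre/post term. Nor is parameters against men a strict test of estimability: two of the outcomes have up to 48 man-visits. The sparse pairwise tables with tolerability are the firmer argument.

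**A reader might infer that the treatment effect as a whole is infinite.** That is also too strong. The protocol does not say that visit is a covariate, and a model of post-treatment or change scores has no such coefficient. With visit included, only contrasts with full retraction diverge. All the phimosis contrasts diverge only if full retraction is the reference grade. The endpoint in Section 4.4 is improvement in retraction, of which full retraction is only one grade.

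**A reader might infer that every joint model fails.** It does not. A proportional-odds version with one association per pair needs 3 × 4 + 3 + 3 = 18 parameters at K = 5, even with a visit term for all three outcomes.

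**The Statistical Plan may help.** Section 8 summarises a plan that is not shown, and which may collapse categories, restrict associations or use penalised fitting. Penalised fitting would return finite values, though in data this sparse they would lean on the penalty. The protocol states none of these.

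**Conclusion.** The point holds in a conditional form, as a minor one. The unordered joint model named in Section 8.2 is not supportable in 24 men for scales of about four or more levels each. Three levels remain fragile, given the 45% chance of an empty cell per table. The parameter counts and empty-cell chances rest on assumed equal level counts and unrestricted pairwise associations.

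The contradiction on tolerability rests on no assumption. Section 8.2 has it measured before and after treatment, while Sections 6.2, 6.8 and 7.1 collect it only at the end.

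The divergence at full retraction rests on two conditions: that visit is a covariate, and that at least one man reaches that grade. The separate ordinal regressions are not affected in this way, and the primary endpoint does not depend on the joint model.

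**What to change.** - Delete the joint multinomial sentence from Section 8.2, and its counterpart in the Statistical Plan if there is one.
- Keep the separate ordinal analyses.
- Correct Section 8.2 so that tolerability is listed as measured after treatment only, in line with Sections 6.2, 6.8 and 7.1.
- If a joint view is wanted, report Kendall or Spearman correlations between phimosis change, quality-of-life change and the tolerability score, with bootstrap intervals.

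The cost is a small text change, with no extra data or participants. The downside is that no model-based joint statement on the three outcomes will be available.
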